6 TREATMENT PROCEDURES

6.1 DRUG PREPARATION AND ADMINISTRATION.

- **Carfilzomib** for Injection is supplied as a lyophilized parenteral product in single-use vials. The lyophilized product is reconstituted with Sterile Water for Injection to a final carfilzomib concentration of 2.0 mg/mL prior to administration. Refer to Study Manual for full instructions. The dose will be calculated using the subject's actual BSA at baseline, or Day 1. Subjects with a BSA > 2.2 m² will receive a dose of carfilzomib based upon a 2.2 m² BSA.
- For subjects considered at risk for TLS, oral hydration may be given as follows:
 30 mL/kg/day (approximately 6 to 8 cups of liquid per day) continuing up to the time of treatment.
- IV hydration will be given prior to carfilzomib during Cycle 1. This will consist of 250 to 500 mL normal saline or other appropriate IV fluid given over 30 to 60 minutes. If lactate dehydrogenase (LDH) or uric acid is elevated > 1.5 times IULN (and/or in subjects considered still at risk for TLS) at Cycle 2 Day 1, then the recommended IV hydration should be given additionally before each dose in Cycle 2. The goal of the hydration program is to maintain robust urine output (e.g., ≥ 2 L/day). Subjects should be monitored periodically during this period for evidence of fluid overload. Note: On Days 1, 8 and 15 of cycle 1, irinotecan is given prior to carfilzomib and this satisfies the prehydration requirement, provided the irinotecan is mixed in at least 250 mL of fluid.
- If the subject has a dedicated line for carfilzomib administration, the line must be flushed with a minimum of 20 mL of normal saline prior to and after drug administration.
- Dexamethasone 8 mg PO/IV will be administered prior to all carfilzomib doses during Cycle 1 and after that as described in section 6.5.1.
- Carfilzomib will be given as an IV infusion over approximately 30 minutes. The dose will be administered at a facility capable of managing hypersensitivity reactions. Subjects will remain at the clinic under observation for at least 1 hour following each dose of carfilzomib in Cycle 1 and following the dose on Cycle 2 Day 1. During these observation times, **post dose IV** hydration (between 250 mL and 500 mL normal saline or other appropriate IV fluid formulation) may be given over 30 to 60 minutes. Subjects should be monitored periodically during this period for evidence of fluid overload.

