6.3.3 DOSE REDUCTIONS OF CARFILZOMIB AND IRINOTECAN FOR NON-HEMATOLOGIC TOXICITIES

Dose adjustment guidelines for non-hematologic toxicities that occur at any point during the prior cycle are summarized as follows:

Event name	Recommended Action	Recommended Action
Grade of Event	Carfilzomib	Irinotecan
Allergic reaction/hypersensitivity		
Grade 2 – 3	Hold until ≤ Grade 1, reinstitute at full dose.	No change in dose
Grade 4	Discontinue	No change in dose
Tumor lysis syndrome $(\geq 3 \text{ of following:} \geq 50\% \text{ increase in creatinine, uric acid, or phosphate;} \geq 30\% \text{ increase in potassium;} \geq 20\% \text{ decrease in calcium; or } \geq 2-\text{fold increase in LDH}$	Hold carfilzomib until all abnormalities in serum chemistries have resolved. Reinstitute at full doses.	Hold irinotecan until all abnormalities in serum chemistries have resolved. Reinstitute at full doses.
Infection Grade 3 or 4	Hold carfilzomib until systemic treatment for infection complete. If no neutropenia, restart at full dose. If neutropenic, follow neutropenic instructions.	Hold irinotecan until systemic treatment for infection complete. If no neutropenia, restart at full dose. If neutropenic, follow neutropenic instructions.
Peripheral Neuropathy Grade 2 treatment emergent with pain or Grade 3neuropathy	Continue to dose. If neuropathy persists for more than two weeks hold carfilzomib until resolved to ≤ Gr 2 without pain. Then restart at 1 dose decrement if indicated.**	No change in dose
Peripheral Neuropathy Grade 4 neuropathy	Discontinue	Discontinue
Serum creatinine elevation Grade 2, 3 or 4	Hold until ≤ Grade 1. Resume at one dose level lower, if indicated.**	Hold until ≤ Grade 1. Resume at one dose level lower, if indicated.**

Hepatic Impairment Grade 3 or 4 elevation of transaminases or bilirubin	Hold Carfilzomib until < Grade 2. Resume at one dose level lower, if indicated.**	Hold Irinotecan until < Grade 2. Resume at one dose level lower, if indicated.**
Congestive heart failure Grade 3 or 4	Any subject with symptoms of grade 3 or 4 congestive heart failure, whether or not drug related, must have the dose held until resolution to grade 2 or less, or return to baseline, after which treatment may continue at 1 dose decrement, or the subject may be withdrawn from the study. If no resolution after 2 weeks, the subject will be withdrawn from the study.	No change in dose

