6.4 SAFETY CONSIDERATIONS

Based upon the experience in the Phase 1 and 2 clinical studies with carfilzomib, in approximately 700 subjects, the following observations are noted:

- A "first dose effect" has been seen, which is notable for fever, chills, rigors, and/or dyspnea occurring during the evening following the first day of infusion and an increase in creatinine on Day 2, which may be the clinical sequellae of rapid tumor lysis and/or cytokine release.
- Should a "first dose" effect occur at any point during Cycle 1 or 2, treatment with high dose glucocorticoids (e.g. methylprednisolone 50–100 mg) is recommended. In addition, intravenous fluids, vasopressors, oxygen, bronchodilators, and acetaminophen should be available for immediate use and instituted, as medically indicated.
- Dexamethasone 8 mg PO/IV will be administered prior to all carfilzomib doses during the first cycle and after that as per section 6.5.1. Subjects with active or suspected infection of any kind that required systemic treatment should not be dosed with carfilzomib until the infection has resolved and if being treated with anti-infective, the course of antibiotics has been completed.
- Subjects should have anemia corrected in accordance with the Institutional guidelines.

Carfilzomib and Irinotecan treatment can cause nausea, vomiting, diarrhea, or constipation sometimes requiring the use of antiemetics or antidiarrheals. Fluid and electrolyte replacement should be administered to prevent dehydration. Subjects should be advised about diarrhea caused by Irinotecan and should have loperamide readily available at home.

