£ PD: Carfilzomib proteasome chymotrypsin-like activity in PBMC (LMP7 and b5 activity) and gamma-H2AX and Topoisomerase-I expression Day 1: The sampling times relative to the start of irinotecan infusion: Pre-irinotecan, 90 min, 2 hours, 5.5 hours; Day 2: pre-carfilzomib infusion

& Submit tumor block or 10 unstained slides of pre-existing tumor

@ Follow-up will be for 30 days after last treatment or until all drug-associated (possible, probably or definite) toxicities have resolved to Grade 1 or less

Phase II Study Calendar:

Required Studies		Cycle 1				Cycle 2,4,6					Cycle 3, 5											
-			Day Day																			
	Screen within 2 weeks unless specified	1	2	8	9	15	16	1	2	8	9	15	16	22	1	2	8	9	15	16	Off study	$Follow-up^{@}$
PHYSICAL																						
Informed Consent	X																					
Medical History	Х																					
Physical Examination	X							Х							Х						Х	Х
Performance Status and Weight	Х							Х							Х						Х	Х
Toxicity Assessment								Х							Х						Х	Х
Disease Assessment	X							Х							Х							
RADIOLOGY																						
CT/MRI scan ¶	Х													Х							Х	Х
Brain CT/MRI #	Х																					
ECG#	X																					
LABORATORY																						
CBC w/differential	X*	Х		Х		х		Х		Х		Х			Х		Х		Х		Х	Х
Serum chemistries §	X*	Х		Х		Х		Х		Х		Х			Х		Х		Х		Х	Х
Serum Magnesium	X*	Х						Х							Х						Х	Х
Serum or urine Pregnancy Test	X*																					
TREATMENT																						
Irinotecan √		Х		Х		Х		Х		Х		Х			Х		Х		Х			
Carfilzomib $$ (study provided)		Х	Х	Х	Х	х	Х	Х	Х	Х	х	Х	Х		Х	Х	Х	Х	Х	Х		
Dexamethasone 8 mg		Х	Х	Х	Х	Х	Х															
PK/PD/Correlative																						
Pharmcodynamic blood tests £		X	Х																			
Tissue Submission &	X			1				1		1					1			1				ĺ

¶ CT or MRI (the same method used at prestudy to meet the eligibility criteria in Section 5.3) must be repeated after ever two cycles of treatment until disease progression. Once off study, the frequency of this scan may be reduced to every 3 months until disease progression.

#Prestudy, and then as clinically indicated

* This test is required prestudy within 2 weeks of starting study medication.

§ Sodium, potassium, calcium, chloride, , creatinine, magnesium, SGOT, , alkaline phosphatase, total bilirubin prior to treatment on Day 1 of each cycle (at most 2 days prior to Day 1 of the next cycle); Sodium, potassium, chloride, creatinine, prior to treatment on Day 8 & 15

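### The study calendar does not schedule the LDH, uric acid and phosphate values that the tumor lysis hold rule and the Cycle 2 hydration trigger use; calendar and rules need to be reconciled

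*Combined protocol and SAP*

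**What the plan says.** Two rules in the treatment sections depend on named laboratory values.

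- **Hold rule (Section 6.3.3, tumor lysis row).** Tumor lysis syndrome is declared when at least 3 listed changes are present: a 50% "increase in creatinine, uric acid, or phosphate", a 30% rise in potassium, a 20% fall in calcium, or a doubling of LDH. The action is "Hold carfilzomib until all abnormalities in serum chemistries have resolved", with matching wording for irinotecan. The table is introduced as "Dose adjustment guidelines for non-hematologic toxicities that occur at any point during the prior cycle are summarized as follows".
- **Hydration trigger (Section 6.1).** IV hydration continues before each Cycle 2 dose on this condition: "If lactate dehydrogenase (LDH) or uric acid is elevated > 1.5 times IULN", with a second limb, "and/or in subjects considered still at risk for TLS) at Cycle 2 Day 1".

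Section 7 fixes which chemistries are drawn and when. In the Phase II calendar footnote, Day 1 of each cycle has sodium, potassium, calcium, chloride, creatinine, magnesium, SGOT, alkaline phosphatase and total bilirubin. Days 8 and 15 have only this: "Sodium, potassium, chloride, creatinine, prior to treatment on Day 8 & 15". The Phase Ib footnote adds SGPT on Day 1 and is otherwise the same for this purpose. No other section schedules LDH, uric acid or phosphate.

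**The concern.** A rule that depends on a measurement works on routine data only if the measurement is scheduled. Here three of the six tumor lysis analytes, and both analytes in the laboratory limb of the hydration trigger, appear on no itemised panel. A site that follows the calendar exactly does not obtain the values that it needs to apply these rules as written. Most of the tumor lysis criteria are also relative changes, so a later unscheduled value has no baseline specified by the protocol for comparison.

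The timing adds to this. Section 6.4 describes, after the first infusion, "an increase in creatinine on Day 2, which may be the clinical sequellae of rapid tumor lysis and/or cytokine release", so the protocol places the effect early in Cycle 1. That is the part of treatment in which the scheduled panels carry the fewest tumor lysis components.

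At stake is whether two written safety rules can be carried out, and carried out alike across at least eight sites. The efficacy analysis is not at stake.

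**Working it through.** The plan states no figure on this point. The check compares the analytes that each rule uses with the panels in Section 7.

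**Inputs**
- Threshold for the hold rule: at least 3 components (Section 6.3.3).
- Components: creatinine, uric acid, phosphate, potassium, calcium, LDH. The wording can be read as 6 separate items, or as 4 items if creatinine, uric acid and phosphate count as one. Both counts are shown.
- Hydration analytes: LDH and uric acid, read at Cycle 2 Day 1 (Section 6.1).
- Panels: Day 1, and Days 8 and 15, from the Section 7 footnotes.

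**Components on each scheduled draw**

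| Draw | Components on the panel | Of 6 | Of 4 | Can 3 be reached? |
|---|---|---|---|---|
| Cycle 1 Day 1, before the first dose | potassium, calcium, creatinine | 3 | 3 | No, baseline only |
| Cycle 1 Days 8 and 15 | potassium, creatinine | 2 | 2 | No |
| Cycle 2 Day 1 | potassium, calcium, creatinine | 3 | 3 | Only if all three are abnormal |

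Pooling Days 8 and 15 does not help, because both carry the same two components. The first scheduled draw at which the rule can be met is Cycle 2 Day 1, which is 28 days after the first dose, or 26 if the permitted two-day window is used (28 − 2). From then on, Day 1 panels hold exactly the minimum number, so no measured component may be normal. The answer is the same under both counts.

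**Hydration trigger.** Analytes required: LDH or uric acid. Analytes on the Cycle 2 Day 1 panel: 0 of 2. Only the judgement limb can act on scheduled information.

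**Could text lost from the PDF explain this?** The Phase II Day 1 list has two empty positions between commas, one after chloride and one after SGOT. The second stands where the Phase Ib list has SGPT. The first is unexplained, and the Phase Ib list has nothing there. Two positions cannot hold three missing analytes, but one could hold LDH or uric acid, and the hydration limb needs only one of these. The Day 8 and 15 list has no gap, so the count of 2 stands in any case.

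**The case against.** The case against is substantial, and much of it stands.

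- **Other protection exists.** Section 6.3.3 holds both drugs for Grade 2 to 4 creatinine elevation alone, and creatinine is measured on Days 8 and 15. Other drug-related toxicity of Grade 3 or more also holds both. Section 6.4 manages the first-dose effect without a laboratory trigger, and every subject receives hydration and dexamethasone in Cycle 1. This stands. The creatinine row is not an exact substitute, however: it resumes one dose level lower if indicated, while the tumor lysis row resumes at full dose.
- **Unscheduled labs are allowed.** This is true, and the footnote does not itemise the screening panel, so some sites may hold baseline values. The protocol does not require them.
- **Few cases are expected.** Section 1.3.4 reports four suspected or documented cases before prophylaxis, then none in more than 350 further myeloma subjects. Section 1.3.3 says that prophylaxis essentially eliminated clinically significant events, and Section 9.3.1 lists the syndrome as uncommon. A reader might turn the four cases into an expected rate for this trial. The documents do not support that: the cases predate prophylaxis and come from another disease, and the size of one of the two studies is given as 39 in one place and 54 + 33 = 87 in another.

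Three further inferences are tempting and also fail.

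- **That tumor lysis would be under-counted in the safety endpoint.** Sections 9.1 and 9.3 describe and grade adverse events by CTCAE 4.03, not by the hold rule, and a clinical diagnosis is reportable from any laboratory result.
- **That the rules cannot operate at all.** The hydration trigger has a judgement limb, and Day 1 panels from Cycle 2 onward hold three components.
- **That a Day 2 chemistry is missing.** Section 6.4 mentions Day 2, but no rule in Section 6.1 or 6.3.3 calls for a value on that day.

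**Conclusion.** The point holds as an inconsistency between the calendar and two of the protocol's own safety rules. On scheduled labs, the tumor lysis hold rule has 2 of the 3 components it needs throughout on-treatment Cycle 1. It has exactly 3 at Cycle 2 Day 1. The laboratory limb of the hydration trigger has 0 of 2 analytes at the time it is read.

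The Day 8 and 15 finding is firm. It does not depend on how the component list is counted or on the gaps in the Day 1 list. The hydration finding rests on the Day 1 list as it reads in the available text, and the unexplained position after chloride should be checked against the original page. Both findings assume that a site orders only what the footnote itemises.

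The clinical consequence is limited for the reasons given above, assuming that the myeloma experience with prophylaxis carries over to small cell lung cancer. Six-month survival, its decision rules and its power are untouched.

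**What to change.** Reconcile Sections 6.1, 6.3.3 and 7 so that the analytes each rule uses are measured at the draws where the rule is applied, with a baseline for the criteria written as changes. Whether to align the calendar or the rules is for the sponsor; this review takes no position on the hydration or hold rules themselves.

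One low-cost way is to amend the chemistry footnote at draws already scheduled:

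- Day 1 of Cycles 1 and 2: add LDH, uric acid and phosphate (3 assays per draw).
- Days 8 and 15 of Cycle 1: add the same three and calcium (4 assays per draw).

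This comes to 2 × 3 + 2 × 4 = 14 additional routine assays per subject who reaches Cycle 2, with no new draw days. If the sponsor means the rules to rest on unscheduled labs ordered on suspicion, the protocol should say so. It should also say whether the hold rule is meant to work on scheduled labs in later cycles, where Days 8 and 15 again carry two components.

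Phase Ib enrollment is complete (Section 1.5), so the change concerns the approximately 88 planned Phase II registrations. The cost is a footnote amendment and the extra assays.

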8.2 POST TREATMENT FOLLOW-UP

Phase Ib: All subjects will be followed for 30 days after last treatment and until all drug-associated (possible, probably or definite) toxicities have resolved to Grade 1 or less.

Phase II: All subjects will be followed every 3 months until death or for 2 years after initial registration, or until death, or until study closure whichever occurs first.

9 ADVERSE EVENTS

9.1 ADVERSE EVENTS DEFINITIONS

An AE is any untoward medical occurrence in a study subject administered an investigational product and that does not necessarily have a causal relationship with this treatment.

An AE therefore can be any unfavorable and unintended sign (including laboratory finding), symptom or disease temporally associated with participation in an investigational study, whether or not considered drug-related. In addition to new events, any increase in the severity or frequency of a pre-existing condition that occurs after the subject signs a consent form for participation is considered an AE. This includes any side effect, injury, toxicity, or sensitivity reaction.

A suspected adverse reaction means any AE for which there is reasonable possibility that the drug caused the AE. *'Reasonable possibility'* means there is evidence to suggest a causal relationship between the drug and the AE. An adverse reaction means any AE caused by a drug. This means there is reason to conclude that the study drug caused the event.

An AE or suspected adverse reaction is considered "unexpected" if it is not listed in the current Investigators Brochure (IB) or prescribing information for a marketed compound or is not listed at the specificity or severity that has been observed; or is not consistent with the risk information described in the general investigational plan or elsewhere in the current application. In addition, AEs or suspected adverse reactions that are mentioned in the IB as occurring with a class of drugs or as anticipated from the pharmacological properties of the drug, but are not specifically mentioned as occurring with the particular study drug is considered "unexpected."

This study will utilize the Common Terminology Criteria for Adverse Events (CTCAE) version 4.03 to describe the event and for assessing the severity of AEs (see Appendix D). Any events representing a change in the CTCAE Grade need to be reported on the AE case report form. This includes any change in laboratory values.

Any condition, laboratory abnormality, or physical finding with an onset date prior to the subject signing consent for study participation is considered to be pre-existing in nature and part of the subject's medical history.

9.2 CAUSALITY

Using the following criteria, the relationship of the AE to the study drug should be assessed as follows:

- Yes: The event is suspected to be related if:
 - there is a clinically plausible time sequence between onset of the AE and administration of study treatment; and/or
 - there is a biologically plausible mechanism for the study treatment to cause or contribute to the AE; and/or
 - the event responds to withdrawal of the study medication (dechallenge) and/or recurs with rechallenge (when clinically feasible); and/or
 - the AE cannot be reasonably attributed to concurrent/underlying illness, other drugs, or procedures
- No:
 - the AE is more likely to be explained by the subject's clinical state, underlying disease, concomitant medication, study or non-study procedure; and/or
 - the time of occurrence of the AE is not reasonably related to administration of study treatment; and/or
 - the event is unlikely to be related to the investigational product(s)

9.3 ADVERSE EVENTS REPORTING PROCEDURES

All AEs, any new event with an onset date after the subject signs consent for study participation or changes to any pre-existing abnormalities that occur after initiation of treatment must be promptly documented on the appropriate summary. Details of the event must include severity, relationship to study drug, duration, action taken, and outcome. Serious adverse events (SAEs) will be recorded on the Adverse Events and SAE eCRFs, as part of the CRAB CTC Electronic Data Capture (EDC) system.

CTCAE term (AE description) and grade: The descriptions and grading scales found in the revised NCI Common Terminology Criteria for Adverse Events (CTCAE) version 4.03 will be utilized for AE reporting. All appropriate treatment areas should have access to a copy of the CTCAE version 4.03. A copy of the CTCAE version 4.03 can be downloaded from the CTEP web https://evs.nci.nih.gov/ftp1/CTCAE/CTCAE_4.03/CTCAE_4.03_2010-06-14_QuickReference_8.5x11.pdf Attribution of the AE:

Definite - The AE is clearly related to the study treatment.

Probable – The AE is likely related to the study treatment.

Possible – The AE may be related to the study treatment.

Unlikely – The AE is doubtfully related to the study treatment. Unrelated – The AE is clearly NOT related to the study treatment.

All AEs that are considered possibly, probably or definitely related to study drug must be followed to resolution or stabilization if improvement is not expected.

Baseline abnormalities will be captured as part of the medical history as described in section 9.1. AEs should be reported from the time of consent through 30 days post-last dose of study drug or initiation of a new anti-cancer therapy, whichever occurs first. In addition, the Investigator should report any AE that may occur after this time period that is believed to have a reasonable possibility of being associated with study drug. If a subject is randomized but discontinues study prior to receiving any study drug, AEs must be reported through the end-of-study visit. AEs which completely resolve and then recur should be recorded as a new AE. For subjects who complete the end of study visit less than 30 days following their last dose of study drug, a follow up of ongoing AEs should be attempted by telephone, and documented in the subject's source. AEs continuing at 30 days post-last dose should have a comment in the source by the Investigator that the event has stabilized or is not expected to improve.

The site Principal Investigator is responsible for evaluating all AEs, obtaining supporting documents, and determining that documentation of the event is adequate.

All Grade 3 and 4 laboratory abnormalities must be recorded as AEs on the CRF. Grade 1 and 2 abnormalities should only be recorded if they require treatment or are otherwise considered clinically significant by the Investigator.

The Principal Investigator may delegate these duties to Subinvestigators and must ensure that these Subinvestigators are qualified to perform these duties under the supervision of the Principal Investigator and that they are listed on the FDA Form 1572.

